5.2.1.4 Covariate Interaction

The impact of the covariates will be examined to identify potential parameters that could influence the primary endpoint (ie % liver fat using MRI-PDFF).

CCI

For the categorical covariate, an ANCOVA model which includes the randomized arm, covariate and the randomized arm-by-covariate interaction as independent factors, and log(baseline) value as an additional covariate will be used. If the p -value for the interaction is less than 0.05, the LS means and LS mean differences will be displayed by each level (absence = 0 or presence = 1) of the categorical covariate.

For the continuous variable (eg weight, baseline), an ANCOVA model which includes the randomized arm, covariate and the randomized arm-by-covariate interaction as independent variables, and log(baseline) value as an additional covariate will be used. If the p -value for the interaction is less than 0.05, the LS means and LS mean differences will be displayed at Q1, median, and Q3 levels of the continuous covariate.

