### 4.3. Randomization Criteria

- *At Pre-Qualification*, following completion of informed consent, subjects will be assigned a single 8-digit study-specific subject identification (SSID) number by the IRT (interactive response technology) system which will be retained throughout the duration of participation in the study;
- *At Visit 5 (Day 1)*, IRT will be used to assign each eligible subject a randomization number, with this number recorded on the electronic Case Report Form (e-CRF).
- A computer-generated randomization code using the method of random permuted blocks will be utilized to randomize subjects 1:1:1:1:1 (across placebo or 1 of 4 active doses of PF-05221304) at Visit 5 (Day 1) prior to the first dose of the double-blinded investigational product (PF-05221304 or matching placebo) provided subjects' satisfy **all** the following criteria:
  - Eligibility criteria outlined in [Section 4.1](#) and [Section 4.2](#);
  - A negative urine drug test for illicit drugs for sample collected at Visit 4 (Day -14) and results as reported by sponsor-identified central laboratory;
  - Fasting ( $\geq 8$  hours overnight, with water permitted) serum triglyceride result of  $\leq 400$  mg/dL (4.5 mmol/L), for sample collected at Visit 4 (Day -14), as reported by sponsor-identified central laboratory;
  - In females, *serum* pregnancy test at Visit 4 (Day -14) as reported by sponsor-identified central laboratory **and** *urine* pregnancy test *on-site* (in females of childbearing potential) at Visit 5 (Day 1) as reported on-site using supplies offered by sponsor-identified central laboratory, are negative for pregnancy – refer to [Section 7.3.1](#);
  - Noted to be  $\geq 90\%$  compliant (based on pill count) with the single-blind placebo administered from Visit 4 (Day -14) to *1 day before* Visit 5 (Day 1), inclusive, for a total duration of  $14 \pm 2$  days;
  - Total score of  $< 8$  on the AUDIT questionnaire, as assessed at Visit 5 (Day 1).
- Study will employ 2-tier stratification as outlined in [Figure 3](#).

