## 9.1. Sample Size Determination

The sample size for this study was based on interest to assess a dose-response for effect of PF-05221304 on percent change from baseline in liver fat (entire study population as well as separately in each sub-population in 1st tier stratification) and percent change from baseline in ALT in the 1st tier stratification sub-population of diagnosed/presumed NASH.

The proposed sample size for this study is approximately 360 subjects randomized (72 subjects per arm) to ensure at least 300 subjects (60 subjects per arm) complete the study.

The sample size of a minimum of 60 completers per arm, was calculated to yield  $\geq 80\%$  power to detect a placebo-adjusted, percent change from baseline of  $\geq 30\%$  in liver fat (in entire study population *and* in  $n=30$ /arm in each sub-population of the 1st tier stratification), using a 1-sided, t-test at level 10%. The calculation assumes that the standard deviation for liver fat is 7.8% (between-subject) and 6.2% (within-subject).

For the secondary endpoint of ALT in the 1st tier stratification sub-population of diagnosed/presumed NASH, the sample size of a minimum of 30 completers per arm was calculated to yield  $\geq 80\%$  power to detect a placebo-adjusted, percent change from baseline in ALT of  $\geq 35\%$ , using a 1-sided, t-test at level 10%. The calculation assumes that the standard deviation for the parameter of placebo-adjusted, percent change from baseline in ALT is 55% (between-subject).

Overall, via the planned interim analysis (refer to [Section 9.5](#)), if the observed standard deviation for the liver fat (MRI-PDF) and ALT data, based on unblinded review, is greater than the assumptions above, the sample size for this study *may* be adjusted upward, at sponsor discretion, to a maximum of 500 subjects randomized (ie, 100 subjects per arm).

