6.1.2.2 Covariate-by-treatment interaction

Covariate-by-Treatment interaction will be performed on % Liver Fat at Week 16 on FAS and PPAS (observed cases) as described in section 5.2.1.4.

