9 APPENDICES

Appendix 1. SUMMARY OF EFFICACY ANALYSES

Endpoint	Analysis Set	Statistical Method	Model/ Covariates/ Strata	Missing Data	Interpretation
Percent change from Baseline in % Liver Fat assessed by MRI-PDFD Over Time	FAS and PPAS	MMRM on log-transformed relative change	Treatment, time and treatment-by-week interaction as fixed effects, subject as random effect with log(baseline) as covariate.	No Imputation	Primary Analysis
Percent Change from Baseline in % Liver Fat assessed by MRI-PDFD at Week 16	FAS and PPAS	ANCOVA on log-transformed relative change	Treatment, Weight and treatment-by-Weight interaction as fixed effects, subject as random effect with log(baseline) as additional covariate.	No Imputation	Sensitivity analysis with two covariates on primary endpoint.
Percent Change from Baseline in % Liver Fat assessed by MRI-PDFD at Week 16	FAS and PPAS	ANCOVA on log-transformed relative change	Treatment, concomitant drug and treatment-by-concomitant drug interaction as fixed effects, subject as random effect with log(baseline) as additional covariate.	No Imputation	Sensitivity analysis with two covariates on primary endpoint.
Percent Change from Baseline in % Liver Fat assessed by MRI-PDFD at Week 16	FAS	Dose-Response model	See section 5.2.1.3	No Imputation	Supportive analysis on primary endpoint
Percent change from Baseline in ALT Over Time	FAS	MMRM on log-transformed relative change	Treatment, time and treatment-by-week interaction as fixed effects, subject as random effect with log(baseline) as covariate.	No Imputation	Secondary analysis

Endpoint	Analysis Set	Statistical Method	Model/ Covariates/ Strata	Missing Data	Interpretation
Percent Change from Baseline in ALT at Week 16	FAS	Dose-Response model	See section 5.2.1.3	No Imputation	Supportive Analysis on secondary endpoint
Tertiary endpoints: Change from Baseline over time	FAS	MMRM on change from baseline	Treatment, time and treatment-by-week interaction as fixed effects, subject as random effect and baseline as covariate	No Imputation	Tertiary analysis
Tertiary endpoints: Percent change from Baseline over time other than % Liver Fat using MRI-PDF	FAS	MMRM on log-transformed relative change	Treatment, time and treatment-by-week interaction as fixed effects, subject as random effect and log(baseline) as covariate.	No Imputation	Tertiary Analysis

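### The SAP shows liver-fat effects by covariate level only when the arm-by-covariate interaction has p < 0.05, so a moderate binary effect modifier would usually go undisplayed and one that is displayed would look too large.

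*SAP*

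**What the plan says.** SAP 5.2.1.4 gives the aim of the covariate analysis as "to identify potential parameters that could influence the primary endpoint", namely percent liver fat by MRI-PDFF. Each model is an ANCOVA with randomized arm, the covariate, their interaction and log(baseline).

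The display rule for a categorical covariate is that, if the p-"value for the interaction is less than 0.05, the LS means and LS mean differences will be displayed by each level", with the levels coded "absence = 0 or presence = 1) of the categorical covariate". For a continuous covariate (weight and baseline are the examples given) the same threshold applies, after which "the LS means and LS mean differences will be displayed at Q1, median, and Q3 levels of the continuous covariate". The visible text makes no provision for showing these estimates when p is 0.05 or larger.

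SAP 6.1.2.2 sets the data: "Covariate-by-Treatment interaction will be performed on % Liver Fat at Week 16 on FAS and PPAS", using observed cases. SAP Appendix 1 lists a weight model and a model with "Treatment, concomitant drug and treatment-by-concomitant drug interaction as fixed effects", both labelled as sensitivity analyses on the primary endpoint. SAP 6.4 plans analyses by the first- and second-tier strata and no other subsets. Part of 5.2.1.4, apparently where the covariates are listed, is blacked out, so the content of that list is not at issue here.

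**The concern.** The analysis is a screen, but its results are shown only after a test stricter than the trial's own standard. SAP 5.1 infers on the primary endpoint at one-sided 10%, and SAP 5.2.1.2 reports 80% intervals. Protocol 9.1 sizes the trial for differences from placebo, not for interactions.

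Two things follow if the test has little power. A modifier of moderate size will usually leave no by-level estimate for the reader to judge. And the estimates that do appear are those that happened to come out large, so they overstate how far the drug effect differs between levels. Outside the two strata tiers, this rule is the only visible route in the plan to by-level liver-fat effects.

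**Working it through.** **The plan's own power figure.** Protocol 9.1 claims at least 80% power for differences from placebo and gives no power for any interaction. The ALT claim reproduces as an inequality: difference 35, SD 55, 30 per arm, one-sided 10% gives 88% by the t-test. For liver fat, a difference of 30 against a combined SD of √(7.8² + 6.2²) = 9.96, read literally, gives essentially 100%. Neither says anything about the interaction test.

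**Inputs from the documents**
- Five arms: the plan is to "randomize subjects 1:1:1:1:1 (across placebo or 1 of 4 active doses of PF-05221304").
- 60 analysed per arm: Protocol 9.1 aims "to ensure at least 300 subjects (60 subjects per arm) complete the study", and the analysis uses observed cases at Week 16.
- Two covariate levels, giving (5 − 1) × (2 − 1) = 4 interaction df, tested at 0.05.
- Residual df: 300 − 11 = 289 (ten arm-by-level means plus log(baseline)).

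**Inputs that are assumptions**
- The drug effect differs between levels by δ = 0.5 or 1.0 residual SD, equally at all four active doses.
- A share q of each arm has the covariate: 50%, 30% or 15%.

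**Formula.** In SD units, the level difference within one arm has variance v = 1/(60q) + 1/(60(1 − q)). The five arm-specific differences are (0, δ, δ, δ, δ), whose squared deviations from their mean sum to 4δ² − (4δ)²/5 = 0.8δ². The non-centrality is λ = 0.8δ²/v, and power is P(F(4, 289, λ) > 2.40).

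| Split | v | λ, δ = 0.5 | Power, δ = 0.5 | λ, δ = 1.0 | Power, δ = 1.0 |
|---|---|---|---|---|---|
| 50:50 | 0.0667 | 3.00 | 24% | 12.00 | 80% |
| 30:70 | 0.0794 | 2.52 | 21% | 10.08 | 71% |
| 15:85 | 0.1307 | 1.53 | 14% | 6.12 | 47% |

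A separate simulation of the ANCOVA with a baseline covariate gave 24.4% for the 50:50, δ = 0.5 case.

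**Size of estimates that pass.** I simulated the five arm-specific differences 400,000 times with true δ = 0.5 and kept the runs with p < 0.05. The average pooled active-versus-placebo interaction was 0.80 SD (50:50), 0.85 SD (30:70) and 0.97 SD (15:85). Divided by 0.50, these are 1.6, 1.7 and 1.9 times the truth.

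**Sensitivity of the δ = 0.5 result**
- All 72 randomized per arm analysed: power 29%, 24% and 16% for the three splits.
- Other dose patterns, 50:50, 60 per arm: a difference rising linearly over the doses to 0.5 SD is missed 81% of the time; one confined to the top two doses, 65%.
- Continuous covariate, 300 analysed: missed 21–32% of the time if 0.5 SD is the change per 1 SD of the covariate, or 50–60% if it is the change from Q1 to Q3. With 360 analysed: 13–23% and 41–52%.

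**Precision if everything is shown.** At 50:50 each level has 30 per arm, so a dose-versus-placebo effect within a level has SE √(2/30) = 0.258 SD and an 80% half-width of 1.28 × 0.258 = 0.33 SD. For the interaction at one dose the half-width is 1.28 × √(2 × 0.0667) = 0.47 SD.

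**The case against.** A reader might infer that the plan treats a covariate with p of 0.05 or more as having no influence, or concludes that the drug effect is consistent across its levels. The documents do not support that. SAP 5.2.1.4 conditions only the display of by-level LS means and differences; it attaches no conclusion to a non-significant result and does not withhold the model output or p-value. Nor are all covariate effects behind the condition, since analyses by the two strata tiers are planned separately in SAP 6.4.

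The power range also depends on chosen inputs. Half an SD, the splits and an equal difference at every dose appear nowhere in the documents. On a literal reading of Protocol 9.1 the target effect is about 30/9.96 = 3 SD, so half an SD is about one-sixth of it. A modifier of 1.5 SD would be detected with 99%, 98% and 85% power at the three splits. (If the stated SDs are absolute PDFF points, this scaling needs a baseline mean that the documents do not give.) The covariates named as examples in the visible text of 5.2.1.4 are continuous, where the test does better.

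A general 4-df test is also a reasonable choice in a dose-ranging trial. A 1-df contrast of all active doses against placebo would have 41% power at 5% in the 50:50, 0.5 SD case, but it favours the assumption of equal modification at every dose. A strict threshold for an unadjusted screen can be defended too.

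All of this stands as a limit on the point. It does not answer the narrower matter: a threshold on display hides moderate modifiers and selects for overestimates, and nothing in the plan requires it.

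**Conclusion.** The point holds as a reporting weakness in an exploratory analysis. For a binary covariate with 60 completers per arm and an assumed 0.5 SD difference in drug effect at all four doses, by-level estimates would be displayed only about 14–24% of the time (47–80% for 1.0 SD). When displayed, the 0.5 SD difference would be overstated about 1.6 to 2 times. These figures rest on the assumed effect size, split and dose pattern, and they are not a property of the test for continuous covariates.

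The choice of a 4-df test is not a fault. The primary MMRM, the dose-versus-placebo comparisons and the Emax model do not depend on this rule, and no visible text ties a decision to it. The change is worthwhile but optional.

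**What to change.** In SAP 5.2.1.4, delete the p < 0.05 condition for both categorical and continuous covariates. For every pre-listed covariate, report the placebo-adjusted effects by level, or at Q1, median and Q3, with 80% CIs, alongside the interaction p-value. Label the tables exploratory and add a note that a non-significant interaction is not evidence of no influence. Keep the 4-df test; a 1-df contrast may be added but is not needed.

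The cost is SAP wording and additional table rows, whose number depends on the covariate list, which is not visible. The downside is more exploratory subgroup estimates to read, many with wide intervals; the label and the CIs make that plain.

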5.2.1.2 Longitudinal Analysis

The over time effect of PF-05221304 on primary, secondary, and tertiary endpoints (see list in section 3) will be analyzed using the MMRM approach with randomized arm, time and randomized arm by-time interaction as fixed effects, subject as random effect using unstructured (UN) covariance structure. Baseline (in raw scale or log scale depending on the endpoint) will be included as covariate in the model.

Other covariance structures (eg Compound Symmetry (CS), Autoregressive(1) [AR(1)], Heterogeneous CS (CSH), and Heterogeneous AR(1) [ARH(1)]) will be considered if convergence in the previous model is not met.

The effect of PF-05221304 doses at all **post-randomization** visits will be estimated by the least-square (LS) means as well as LS mean differences against placebo respectively from the model described above.

For all analyses performed on log-transformed relative change from baseline (RCBL), the LS mean estimates and their corresponding confidence intervals (CIs) will be obtained for each randomized arm and week. Differences (and corresponding confidence intervals) between LS mean estimates will be obtained comparing randomized arms for each week. All LS means and LS mean differences (including CI's) will be back transformed to provide adjusted geometric LS means and ratios of adjusted geometric LS means. Then, percent change from baseline will be calculated as follows:

$$\text{Percent change} = 100 * (\text{RCBL} - 1)$$

where RCBL is either the adjusted geometric LS means estimate or the ratio of adjusted geometric means coming from the statistical model. The corresponding 80% CIs will be calculated as well.

For all analyses performed on raw scale, the LS means estimates and their corresponding confidence intervals (CIs) will be obtained for each randomized arm and week. Differences (and corresponding confidence intervals) between LS means will be obtained comparing randomized arms for each week.

Regardless if the data are analyzed in raw scale or after log-transformation, the inter- and intra-subject variability from the statistical model will be available and reported.

For % liver fat assessed by MRI-PDFP analyzed on log-scale, 80% confidence intervals will be presented for the LS geometric mean ratio.

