6.1.1 Primary Analysis on % Liver Fat assessed using MRI-PDF

Population: Entire Study Population

Endpoint: Relative change from baseline

Parameters: % Liver fat assessed with MRI-PDFP:

- Analysis time points: **all** applicable **post** Day 1/Visit 5 time points where **scheduled** assessment of specific continuous parameter is outlined in protocol
- Analysis population: FAS and PPAS (as sensitivity analysis).
- Analysis methodology: Log transformed relative change from baseline will be analyzed using MMRM model with log(baseline) as a covariate (specified in section 5.2.1.2).

Reporting results:

- Raw data and percent changes from baseline: Randomized subject, number of subject contributing to summary, sample size, mean, standard deviation, median, minimum, maximum, Q1 and Q3 at baseline and post-baseline visits will be presented for each randomized arm (see Appendix 2 for further detail).
- MMRM Outputs:
 - ✓ Adjusted geometric LS mean estimates with 80% confidence interval for each randomized arm along with the translation in percent change over time,
 - ✓ Ratio of adjusted geometric LS mean estimates for each active randomized arm against placebo and the corresponding 80% confidence interval along with the translation in percent difference over time.

Figures from MMRM outputs:

1. Line plot of percent change from baseline after back transformation of adjusted geometric LS means with 80% confidence interval over time (see Appendix 3.3),
2. Line plot of percent change from baseline placebo-adjusted after back transformation of adjusted geometric LS means ratios with 80% confidence interval over time (see Appendix 3.4),
3. Percent change from baseline after back transformation of adjusted geometric LS means with 80% confidence interval at Week 16 (see Appendix 3.5),
4. Percent change from baseline placebo-adjusted after back transformation of adjusted geometric LS means ratios with 80% confidence at Week 16 (see Appendix 3.6).

Note regarding the figures:

Instead of producing 4 independent figures, and in order to having a better understanding of the placebo effect, 1 figure containing side-by-side two panels presenting bullet 1 and 2 outputs (right panel for response over time and left panel for placebo adjusted response over time), and 1 figure with two panels presenting side-by-side bullet 3 and 4 outputs (right panel for response at Week 16 and left panel for placebo adjusted response at Week 16) should be produced.

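### SAP 5.2.1.4: if baseline liver fat is the covariate tested, it enters the ANCOVA as both a raw and a log term, and the per-arm LS means at its outer quartiles may describe no possible subject (minor)

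*SAP*

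**What the plan says.** SAP section 5.2.1.4 describes how covariates are examined for influence on the primary endpoint. For a continuous covariate: "For the continuous variable (eg weight, baseline), an ANCOVA model which includes the randomized arm, covariate and the randomized arm-by-covariate interaction". The sentence continues: "as independent variables, and log(baseline) value as an additional covariate will be used". Baseline is written without the log when it is named as the covariate and with the log when it is named as the added term. Nothing exempts baseline from the added term.

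The display rule applies when the p-"value for the interaction is less than 0.05". In that case "the LS means and LS mean differences will be displayed at Q1, median, and Q3 levels of the continuous covariate". No value is given at which log(baseline) is to be held.

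Section 6.1.2.2 applies this to Week 16 liver fat in the FAS and the PPAS, as a supportive analysis. The primary model in section 6.1.1 uses the log scale: "Log transformed relative change from baseline will be analyzed using MMRM model with log(baseline) as a covariate". Section 5.2.1.2 says of the general longitudinal model: "Baseline (in raw scale or log scale depending on the endpoint) will be included as covariate in the model". Appendix 1 lists interaction ANCOVAs for weight and for concomitant drug, with no row for baseline. Part of section 5.2.1.4 is redacted, so the full covariate list cannot be seen.

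**The concern.** For weight the specification is sound: weight is tested, and log(baseline) adjusts for starting liver fat. For baseline liver fat, the tested covariate and the adjustment are the same measurement on two scales. Moving the raw term to a quartile while the log term stays at its mean describes a subject with two different baselines.

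The per-arm LS means are an explicit planned output of the analysis that asks whether response depends on starting liver fat. A reader would take the placebo row as the natural drift or regression to the mean at low and high baseline, and the active rows as the expected response there. Those rows could be wrong in size or in direction.

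**Working it through.** The documents give no figure to reproduce, so the check is algebra followed by worked examples.

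**Inputs.** Model, display points and trigger: SAP 5.2.1.4. Response, the log of relative change from baseline: SAP 6.1.1. 60 completers per arm and a between-subject liver fat SD of 7.8: Protocol 9.1. The baseline distributions, slopes, residual SDs and effect sizes below are assumptions.

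**Algebra.** Let B be raw baseline, i the arm, q a quartile of B and m the mean of log(B). Read literally, the model is y = a_i + (b + c_i)B + g·log(B).

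- Displayed LS mean, with log(B) at its mean: a_i + (b + c_i)q + g·m.
- Coherent LS mean, both terms at the same baseline: a_i + (b + c_i)q + g·log(q).
- Coherent minus displayed: g(log q - m). This is the same for every arm.
- Difference from placebo: (a_i - a_0) + (c_i - c_0)q in both cases, because the g term cancels.

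**Collinearity.** For a lognormal baseline with SD 7.8, truncated at 6%, and means of 15, 18 and 22%, raw and log baseline correlate at 0.954, 0.961 and 0.971 (variance inflation 11.0, 13.0 and 17.3).

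**Noise-free example.** Mean baseline 18%: quartiles 12.6, 16.6 and 21.9%, geometric mean 16.67%. Take g = -0.3, with raw-scale arm slopes that rise with dose. Placebo is displayed at +2.3% throughout.

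- First quartile: -0.3 × ln(12.6/16.67) = +0.0840; 1.023 × e^0.0840 = 1.113, or +11.3%.
- Third quartile: -0.3 × ln(21.9/16.67) = -0.0819; 1.023 × e^-0.0819 = 0.943, or -5.7%.

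| Arm | Displayed (1st quartile, median, 3rd quartile) | Coherent |
|---|---|---|
| Placebo | +2.3, +2.3, +2.3% | +11.3, +2.5, -5.7% |
| Lowest dose | -10.6, -8.6, -5.9% | -2.8, -8.5, -13.3% |
| Highest dose | -62.0, -59.9, -56.8% | -58.7, -59.8, -60.2% |

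The median row is almost right. The direction across quartiles is reversed for both active doses shown and lost for placebo. The contrast survives: at the third quartile, lowest dose over placebo is 0.941/1.023 = 0.92 as displayed and 0.867/0.943 = 0.92 coherently.

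**Simulation, response linear in log(baseline).** 60 per arm, median baseline 16%, log SD 0.45, residual SD 0.4, slope on log(baseline) -0.3 on placebo and -0.7 on every active arm. The outer quartiles lie 0.6745 × 0.45 = 0.3035 from the median on the log scale.

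- True placebo: e^(0.3 × 0.3035) = 1.095 and e^(-0.3 × 0.3035) = 0.913, or +9.5% and -8.7%.
- Displayed placebo: about -10% and +8% in trials where the interaction p-value is below 0.05 (about -9% and +7% over all trials).
- Top dose: displayed -49% and -51%; true -38% and -60%.
- Top dose versus placebo at the three points: -43.6, -48.4 and -54.1%; true -43.6, -50.0 and -55.7%.

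The placebo reversal has a simple cause. The shared log slope is drawn towards the average over arms, (-0.3 + 4 × -0.7)/5 = -0.62. Placebo's raw slope turns positive to compensate, and fixing log(baseline) leaves only that compensation on display.

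**Simulation, response linear in raw baseline.** With the same slopes on raw baseline, placebo is displayed at about +7% and -9% against a true +8% and -10%. The fitted log term is then close to zero and no reversal occurs.

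**Simulation, equal slopes of -0.3 on log(baseline).** Placebo is displayed near 0% at both outer quartiles instead of about +9% and -9%, but the display rule is met in only about 5% of trials.

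**The case against.** The strongest objection is that the faulty model may not be planned at all. Baseline appears once, in a parenthesis of examples beside redacted text, and could conceivably mean baseline weight. Appendix 1 has no baseline row and labels its interaction models as having two covariates, which does not fit baseline tested beside its own log. Section 5.2.1.2 lets the scale of baseline follow the endpoint. If the covariate is therefore log(baseline), the added term is an exact duplicate, it drops out, and the LS means are coherent. Holding log(baseline) at its mean is also a software default, not an SAP instruction. All of this stands. It makes the point conditional, but it does not make the sentence safe to program as written.

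A reader might infer that the trend in treatment effect across baseline is reversed. The documents do not support that: log(baseline) has no interaction with arm, so it cancels from every difference from placebo. The small departures in the simulated contrasts come from fitting a raw-scale interaction to a log-scale truth.

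A reader might also infer that the interaction test loses power. That depends on the unknown true scale: 64% as written against 69% with a log interaction when the truth is log-linear, but 78% against 76% when it is linear in raw baseline. No power claim is made.

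**Conclusion.** The point holds as a minor correction. It rests on two conditions: that baseline in section 5.2.1.4 means raw baseline liver fat, and that log(baseline) is left at its mean. The per-arm LS means at the first and third quartiles are then incoherent. How far they mislead depends on how response relates to baseline: a reversal of the placebo row in the log-linear example, close to no error if the relation is linear in raw baseline. The percentages depend on the assumed slopes and spread; the algebra does not.

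Differences from placebo, the apparent effect modification, the median row and the primary MMRM are not materially affected. The analysis is supportive, its display is conditional, and neither section 5.2.1.4 nor 6.1.2.2 attaches a decision rule to it.

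**What to change.** Add one sentence to SAP section 5.2.1.4: when baseline liver fat is the covariate tested, the model contains arm, log(baseline) and the arm-by-log(baseline) interaction, with no separate raw baseline term, and LS means and differences are reported at the logs of the first quartile, median and third quartile. Keep the stated model for weight and the other covariates. This matches the scale of the primary model.

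The cost is one sentence and a small programming change, with no extra data and no extra patients. If baseline liver fat was never meant to be tested, removing it from the examples settles the matter.
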